## Study Protocol

This experiment will test the app for proof of concept on older subjects with dizziness in a clinical environment (laboratory or clinic) under the supervision of a clinician. The aim is to test whether when using the app older patients perform rehabilitation in a similar manner as when directly instructed by a clinician. A secondary goal is to evaluate usability and enjoyment of the app. Data will be collected on 40 subjects (20 male and 20 female). Subject inclusion criteria are to be aged between 60 and 75, able to walk and get up from a chair independently, free of musculoskeletal disorders, and not taking any medication that may affect balance. Each participant will be asked to take part in two visits. One for the experimental trial and the other for a focus group follow up.

The subject age, body height and mass and vestibular condition will be recorded. They will also be asked to answer a Dizziness Handicap Inventory (DHI) as well as an Activities-specific Balance Confidence (ABC) scale questionnaire to assess how much they are affected by their vestibular condition.

Each subject will perform a rehabilitation session with the prototype app and one session without the app. The session will be setup on the app by the clinician for each participant specifically. The session without the app will include the same exercises at a similar recommended speed and range of motion. These will be performed without any feedback as they would typically be performed by a patient doing their at-home exercises. The order in which the sessions occur will be randomized to avoid learning effects. Subjects are encouraged to take a break between the sessions and can take a break at any time if desired. Each session will start with the participant practicing the games and exercises using the slower speed practice games and proceed when they feel ready. A physical therapist will be present to assist if needed. This is to simulate first use of the app. It is envisioned that the first time a patient will use the app this will be under supervision and assistance of a physical therapist. Patients will perform a full rehabilitation session, lasting about 20 minutes after that.

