Cover page

Official Title of the study: Individualized Vestibular Rehabilitation for Elderly With Self-Management and Gaming Elements

NCT number (if available): STUDY00148324

Date of the document: 3/4/2022

Statistical Design and Power

Number of subjects expected to enroll: 40

Expected effect size and power:

The expected effect size in head range of motion outcome measures (Flexion angle, Extension angle, Left angle, Right angle) is 5°. This is based on the mean and standard deviations of the data that were collected on 6 older vestibular patients in Phase I.

Using an estimated standard deviation of 7.5° and a desired power of 80% and a p<0.05, this resulted in an estimated 36 subjects being required to reach this power.

The expected effect size in head velocity outcome measures (Flexion angular velocity, Extension angular velocity, Angular velocity left, Angular velocity right) is 20°/s. This is based on the mean and standard deviations of the data that were collected on 6 older vestibular patients in Phase I.

Using an estimated standard deviation of 30°/s and a desired power of 80% and a p<0.05, this resulted in an estimated 35 subjects being required to reach this power.

Since effect size of the balance related outcome measures are unknown (these were not calculated in phase I), as well as the differences that will occur due to feedback (hypothesis 6) being unknown, a total number of 40 subjects was decided upon.

Statistical methods:

All outcome measures will be tested for normal distribution using a Kolmogorov-Smirnov test and if required non-parametric tests will be used. Statistical significance will be defined as p<0.05.

Hypothesis 3 will be test for significant difference for outcome measures for the exercises between performing the exercises with and without the app. This will be tested using a paired t-test. The two different conditions for the paired t-test are the exercises performed with and without the app. The outcome measures that will be compared between the two conditions are: Flexion angle, Extension angle, Left angle, Right angle, Flexion angular velocity, Extension angular velocity, Angular velocity left, Angular velocity right, Balance excursion medio-lateral, and Balance excursion anterior-posterior.

If any variable shows a non-normal distribution a Wilcoxon signed rank test will be used instead of a t-test.

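### Session order is randomised, but the Hypothesis 3 tests leave it out; a period term with balanced orders costs almost nothing, and the practice wording for the no-app session needs reconciling

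*SAP*

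**What the plan says.** The protocol (Study Protocol) sets up a within-person comparison: "Each subject will perform a rehabilitation session with the prototype app and one session without the app". On order it says "The order in which the sessions occur will be randomized to avoid learning effects". The gap between sessions is left to the participant: "Subjects are encouraged to take a break between the sessions and can take a break at any time if desired". Neither document gives an allocation method, a ratio or any blocking.

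The SAP (Statistical methods, Hypothesis 3) compares ten outcomes by paired t-test: "The two different conditions for the paired t-test are the exercises performed with and without the app". The fallback is "If any variable shows a non-normal distribution a Wilcoxon signed rank test will be used instead of a t-test". Order, period and sequence appear nowhere in the SAP.

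On practice, the protocol says "Each session will start with the participant practicing the games and exercises using the slower speed practice games and proceed when they feel ready", and shortly afterwards explains: "This is to simulate first use of the app". Of the exercises in the no-app session it says "These will be performed without any feedback as they would typically be performed by a patient doing their at-home exercises".

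**The concern.** The protocol names learning as the reason for randomising order, and the analysis then does not use order. Randomising keeps the estimate unbiased over hypothetical repetitions. It does not remove a first-to-second-session shift from the data of this one trial.

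- With equal numbers in the two orders, the shift cancels from the mean difference but inflates its estimated variance. The test becomes conservative and loses power.
- With unequal numbers, part of the shift stays in the estimate.

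A conservative test is less reassuring here than usual. The stated aim is to see whether patients perform similarly with and without the app, so lost power makes a non-significant result, and hence an apparent finding of similarity, more likely.

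The practice wording is a separate matter. Read literally, participants allocated to the no-app session first would use the app's games before their no-app measurement. That could draw the two conditions together.

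**Working it through.** **Inputs.** From the SAP: N = 40; range-of-motion effect δ = 5°; SD 7.5°; 80% power; p < 0.05 (taken as two-sided); stated requirement 36. Assumed: period shift P (second session minus first) of 0, 2.5 or 5°, the last being as large as the whole expected app effect; normal errors.

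**Which SD the SAP's figure implies.** (1.96 + 0.8416)² × 2 × 7.5² / 5² = 35.3, rounded up to 36. This reproduces the stated number and corresponds to an SD of paired differences of 7.5 × √2 = 10.6°. If 7.5° were itself the SD of differences, a paired t-test would need about 20. Both readings are carried forward.

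**Model.** Let d be app minus no-app. Its mean is δ − P for participants who do the app first and δ + P for those who do it second.

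**Equal orders (20/20).** The mean of d is δ, but the variance seen by the unadjusted test is about SD² + P².

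- SD 7.5°, P = 2.5°: (56.25 + 6.25)/56.25 = 1.11, like having 40/1.11 = 36 participants.
- SD 7.5°, P = 5°: (56.25 + 25)/56.25 = 1.44, like 28.
- SD 10.6°, P = 2.5°: (112.5 + 6.25)/112.5 = 1.06, like 38.
- SD 10.6°, P = 5°: (112.5 + 25)/112.5 = 1.22, like 33.

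Power by simulation at 20/20 (at least 100,000 replicates per setting):

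| SD of differences | Test | P = 0 | P = 2.5° | P = 5° | With period, any P |
|---|---|---|---|---|---|
| 7.5° | t | 0.98 | 0.98 | 0.96 | 0.98 |
| 7.5° | Wilcoxon / rank-sum | 0.98 | 0.97 | 0.95 | 0.98 |
| 10.6° | t | 0.83 | 0.81 | 0.77 | 0.83 |
| 10.6° | Wilcoxon / rank-sum | 0.81 | 0.80 | 0.74 | 0.81 |

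At P = 5° the unadjusted type I error is 0.02 (SD 7.5°) or 0.03 (SD 10.6°). The adjusted tests stay at about 0.05.

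**Unequal orders (24/16).** The estimate moves by (24 − 16)/40 × P = 0.2P, which is 1° at P = 5°, so it centres on 4° or 6° depending on which order is over-represented. At P = 5°:

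- SD 7.5°: unadjusted t-test power 0.82 or 0.99, against 0.98 with a period term.
- SD 10.6°: 0.56 or 0.91, against 0.81 with a period term.
- Unadjusted type I error is 0.06 to 0.07. The adjusted estimate centres on 5° with type I error 0.05.

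Under simple randomisation, a split of 24/16 or worse has probability 2 × P(X ≤ 16), X ~ Binomial(40, 0.5), = 0.27. That is one scenario, since the method is not stated.

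**Averaged over simple randomisation, SD 10.6°.** Unadjusted t-test power is 0.83, 0.81 and 0.74 at P = 0, 2.5 and 5°, against about 0.82 at each P with a period term. Unadjusted type I error stays at about 0.05.

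**Cost of the term when P = 0, SD 10.6°.** At 20/20, t-test power goes from 0.8283 to 0.8278, and the rank test loses about 0.005. Without balance the cost rises: 0.812 at 24/16 and 0.792 at 26/14.

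**Practice wording.** Three statements do not sit together: practice games come before each session; the practice mimics first use of the app; and the exercises in the no-app session are done as at home, with no feedback. If the games are meant only for the app session, the word covering each session is too wide. If they come before both, the no-app condition includes exposure to the app.

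**The case against.** The strongest reply is that nothing is invalid. Order is randomised, participants practise until they feel ready, breaks are encouraged, and averaged over simple randomisation the paired t-test keeps its 5% error rate. The period shift is unknown, and the visible losses need a shift close to the whole expected effect. At 2.5° with balanced orders the loss is two points at most. Under simple randomisation with no shift, the period term costs about one point of power. The large 24/16 contrasts condition on one unlucky split, and blocking alone would remove them without any change to the test.

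Most of this stands, and it limits the point to an efficiency improvement. It does not remove it. After blocking, the unadjusted t-test still gives up between 0 and 0.06 of power, and the term that recovers it costs less than 0.001. The term is near-free only when the orders are balanced, so the two changes belong together.

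On the practice sentence, one can read it as each session rehearsing its own content, with the absence of feedback describing the exercises and not the rehearsal. That reading is possible, but the reference to the games and the first-use rationale leave the ambiguity in place.

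**Conclusion.** The concern holds, and its consequence is modest. The planned tests for Hypothesis 3 are valid on average but do not use the order that the trial randomises. With 20/20 orders, the t-test power loss at a shift of up to 5° is 0 to 0.03 if the SD of differences is 7.5°, and 0 to 0.06 if it is 10.6°. With a chance 24/16 split, each Hypothesis 3 estimate can be off by a fifth of the shift for that outcome. These sizes rest on an assumed shift that the documents do not supply; if it is near zero, nothing is lost and nothing is gained. The practice wording is a genuine ambiguity whatever the shift, and its effect cannot be quantified from the documents. A period term would not correct it, nor would it correct carry-over of app experience into a later no-app session.

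**What to change.** 1. Analyse Hypothesis 3 with condition and period: a mixed model with a random participant effect, or the two-sequence crossover t-test on the paired differences.
2. Replace the signed rank fallback with a rank-sum test that compares first-minus-second-session differences between the two orders.
3. State the allocation method and allocate the two orders 20/20 in blocks.
4. Reconcile the protocol's sentences on practice, first use and the no-app session, so that it is clear what practice precedes the no-app measurement.
5. If a first-session-only comparison is shown, keep it descriptive. It is between persons, 20 against 20, with power of about 0.54 for 5° if the per-session SD is 7.5° (5/7.5 = 0.667).

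The cost is some SAP wording, a blocked list, one clarified protocol passage and one degree of freedom. The sample size stays at 40.

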Hypothesis 4 will be tested using the following outcome measures: Ease of use rating, Enjoyment rating, Motivation rating, Use intention rating, and Usefulness rating. It will be tested whether the mean and median for each of the outcome measures is a positive response (value < 4).

Hypothesis 5 will be tested similar to hypothesis 1 by calculating the accuracy of identifying the errors using the identification by the clinician as gold standard. The goal is to get a minimum accuracy of 90% for each specific error. This does not involve any specific statistical tests.

Hypothesis 6 will be using a paired t-test with pre- and post-feedback as conditions. Dependent variables will be average head range of motion and velocity and standard deviation of velocity over a time window pre- and post-feedback. This will be calculated for each common error separately. It will be tested if head motion is altered for the error of moving the body versus the head, it will be tested whether head motion slows down or speeds up as instructed by the

feedback and if movement velocity standard deviation reduces when feedback is given on an inconsistent speed.

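### Hypothesis 4 has only a cut-off (mean and median below 4) and no named test or confidence bound; if the cut-off decides, its false-pass rate is uncontrolled

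*SAP*

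**What the plan says.** The SAP, under Statistical methods, lists the Hypothesis 4 outcomes as "Ease of use rating, Enjoyment rating, Motivation rating, Use intention rating, and Usefulness rating". The whole of the analysis is then one sentence: "It will be tested whether the mean and median for each of the outcome measures is a positive response (value < 4". The number of scale points, the anchors, the number of items per rating and the meaning of 4 are not given. Nor is it said whether one, some or all of the five ratings must meet the criterion.

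Three other statements bear on how that sentence is read:

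- A general alpha: "Statistical significance will be defined as p<0.05".
- A general fallback: "All outcome measures will be tested for normal distribution using a Kolmogorov-Smirnov test and if required non-parametric tests will be used".
- For Hypothesis 5, which has a 90% accuracy target: "This does not involve any specific statistical tests". No such sentence follows Hypothesis 4.

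Hypotheses 3 and 6 each name a paired t-test. The planned size is given as "Number of subjects expected to enroll: 40". The Study Protocol makes usability and enjoyment of the app a secondary goal.

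**The concern.** The only criterion written down compares two sample summaries with a fixed number. Sampling error does not enter it. If it is applied as a decision rule, the trial could report that older patients rate the app positively when the population is indifferent, and the chance of that error would be fixed by the shape of the answers and not by design. If a test was intended, two analysts could not be expected to run the same one, because the null value, the direction and the roles of the mean and the median are all left open. Either way, the conclusion on a stated goal of the study is not pinned down before the data are seen.

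**Working it through.** **Nothing to reproduce.** The documents give no error rate, power or sample size for Hypothesis 4. The calculation that begins "Using an estimated standard deviation of 7.5° and a desired power of 80% and a p<0.05" concerns head range of motion, so the 40 subjects were not chosen with the ratings in mind.

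**Inputs from the SAP.** n = 40; five ratings; mean < 4 and median < 4 for each.

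**Assumptions not in the documents.** 4 is the neutral point; single items run from 1 to 7; the neutral population is symmetric about 4; all 40 subjects give ratings.

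**Step 1: the median condition, exactly.** With 40 answers the median is the average of the 20th and 21st values. On a single item it can be below 4 only if at least 20 people answer 1–3. Let q be the share answering 1–3 and X ~ Binomial(40, q). P(X ≥ 20) is:

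- q = 0.30 (40% answer 4): 0.6%
- q = 0.35 (30% answer 4): 3.6%
- q = 0.40 (20% answer 4): 13.0%
- q = 3/7 (uniform): 22.5%

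When very few people answer 4 this slightly overstates the pass rate, because a 20th value of 3 and a 21st of 5 average to 4. Simulation is used for those shapes.

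**Step 2: both conditions, by simulation.** The truth is neutral, with 25,000 to 100,000 samples of 40 per row. Shares are for answers 1 to 7.

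| Neutral population | Mean and median < 4 | Upper 95% limit < 4 |
|---|---|---|
| 5, 10, 15, 40, 15, 10, 5% | 0.6% | about 2.5% |
| 5, 10, 20, 30, 20, 10, 5% | 3.7% | about 2.5% |
| 10, 13, 17, 20, 17, 13, 10% | 13% | about 2.5% |
| Uniform | 22% | about 2.5% |
| 10, 15, 20, 10, 20, 15, 10% | 30% | about 2.5% |
| Average of 3 or 4 items | 28%, 32% | 2.4%, 2.3% |
| Continuous normal | 40% | about 2.5% |
| Polarised: 25, 15, 7.5, 5, 7.5, 15, 25% | 39% | about 2.5% |
| Polarised: 30, 15, 4, 2, 4, 15, 30% | 44% | about 2.6% |

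A mildly unfavourable continuous rating (true mean 4.2, SD 1.5) meets the cut-off about 15% of the time.

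**Step 3: five neutral continuous ratings, all required to pass.** If independent, 0.40^5 = 0.010. By simulation the joint rate is 1%, 5%, 9% and 13% for between-rating correlations of 0, 0.3, 0.5 and 0.7.

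**Step 4: what a confidence bound would demand.** The observed mean must lie below 4 − t(0.975, 39) × SD/√40, with t = 2.023.

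- SD 1.5: 4 − 2.023 × 0.2372 = 3.52
- SD 2: 4 − 2.023 × 0.3162 = 3.36

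For a true mean of 3.0 with SD 1.45, the standardised distance is 1/(1.45/√40) = 1/0.2293 = 4.36. The pass probability is about Φ(4.36 − 1.96) = Φ(2.40) = 99%.

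**The case against.** The strongest reply is that the SAP does not say that point estimates decide. It says the criterion will be tested, sets p<0.05 and a non-parametric fallback for all outcome measures, and exempts only Hypothesis 5 from testing. On that reading a one-sample test against 4 is implied and merely unnamed. This stands to the extent that a reader who infers that the SAP declares Hypothesis 4 met on raw point estimates goes further than the text. It does not close the gap. The general sentences supply no null value, direction or procedure, and Hypothesis 5 is also described as being tested before the SAP says that no statistical test is involved. The documented fallback replaces the t-test with a Wilcoxon test, so it does not explain a joint condition on mean and median.

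Three other strong readings also fail:

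- A reader might infer that a sample mean just under 4, say 3.95, is enough. It is not, because the median must also be below 4. That second condition is why the rate can be well below the 48% to 50% that the mean alone would give.
- A reader might infer that a neutral app will almost surely collect a false pass somewhere. For five continuous neutral ratings the chance of at least one pass is indeed 93% if independent and 69% at correlation 0.7. But no passage says that one pass suffices, and the criterion is worded for each measure.
- A reader might infer that the error rate is necessarily high. The scale is not described. With about 30% or more answering exactly 4 on a single item, the cut-off's rate is already under 5%, and at 40% it is lower than that of a confidence bound.

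It is also fair that this is a proof-of-concept study and that no decision in the documents hangs on Hypothesis 4. That limits the consequence. It does not remove the need to say how a stated goal will be judged.

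**Conclusion.** The point holds as a gap in specification with a potentially material effect, on a secondary goal. The SAP's only criterion for Hypothesis 4 is a cut-off on two sample summaries, and how sampling error is to be handled is not stated. If the cut-off decides, the per-rating false-pass rate is not controlled: it runs from under 1% to a little over 40%, depending on a scale and an answer pattern that the documents do not describe. If all five ratings must pass, the joint rate is much lower, about 1% to 13% for continuous scores. All these figures rest on 4 being neutral, symmetric answers and 40 completed ratings; the single-item figures also rest on a 1–7 scale. The change is worth making before analysis but is not critical to the trial.

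**What to change.** Revise the Hypothesis 4 paragraph of the SAP to:

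1. State the scale, its anchors and the number of items per rating, and confirm that 4 is the neutral point and lower values are favourable.
2. For each rating, conclude a positive response only if the upper limit of the two-sided 95% confidence interval for the mean is below 4. If the SAP's normality check fails, use a one-sample Wilcoxon signed-rank test against 4 (two-sided p<0.05, favourable direction), saying how answers equal to 4 are handled. Report the median alongside.
3. State that Hypothesis 4 as a whole is supported only if all five ratings meet this. Otherwise report the ratings individually, without an overall claim. Five independent neutral ratings at 2.5% each would still give 1 − 0.975^5, about 12%, for at least one pass.

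If no inference is intended, label Hypothesis 4 descriptive, report means and medians with intervals, and draw no conclusion from the cut-off.

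The cost is a few sentences, with no extra subjects or data. In most cases the bar rises somewhat: the observed mean must be at or below about 3.52 at SD 1.5, or 3.36 at SD 2. A well-liked app is hardly affected, since a true mean of 3.0 with SD 1.45 would still pass about 99% of the time per rating.

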The real-time feedback during the exercises will be tested. A clinician who is blinded to the feedback the patient receives (as in they cannot see the screen and will be listening to music on headphones in the case of auditory feedback) will identify each error the patient makes and will make notes whether this error continues or is corrected by the patient. This will be coded with numbers and recorded on video. Errors identified by the ML algorithm will be stored in the app as well with a time stamp for comparison. Raw sensor data will be stored and analyzed to test the efficacy of the feedback and see if exercise execution improves after feedback.

IMU data will be collected during both sessions (with and without the app) for comparison. Outcome measures, including range of head motion, movement velocity, and the number of repetitions performed, will be calculated. Data will be compared between the two sessions to investigate whether patients performed exercises similar with and without the app. Questionnaires will be answered to rate usability and enjoyment while using the app, as well as

Questionnaires will be answered to rate usability and enjoyment while using the app, as well as open ended questionnaires to identify areas of improvement.

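### Hypothesis 5 rests on one 90% accuracy figure that these documents do not define, that a poor detector could meet, and that has no planned interval

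*SAP*

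**What the plan says.** In the SAP, under Statistical methods, the plan for this objective is two sentences of method and one goal. The method is "Hypothesis 5 will be tested similar to hypothesis 1 by calculating the accuracy of identifying the errors". What the app's calls are compared with is also given there: "using the identification by the clinician as gold standard". As for the criterion, it reads "The goal is to get a minimum accuracy of 90% for each specific error. This does not involve any specific statistical tests". The goal therefore applies to each error type separately, through one metric, and no interval is mentioned.

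The Protocol (Study Protocol, on real-time feedback) describes the data. A clinician who cannot see or hear the app's feedback "will identify each error the patient makes and will make notes whether this error continues or is corrected by the patient". Of these observations it says "This will be coded with numbers and recorded on video". For the app, "Errors identified by the ML algorithm will be stored in the app as well with a time stamp for comparison".

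Neither document says what the accuracy is a share of, how close in time an alert and a clinician-marked error must be to count as the same event, or how an alert without a clinician mark is scored. The SAP's methods text begins at Hypothesis 3, so the Hypothesis 1 method it relies on cannot be read here.

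**The concern.** A detector that drives real-time feedback can fail in two ways. It can miss an error, so the patient gets no correction, or it can alert when the clinician saw no error, so the patient is corrected without cause. One accuracy figure does not separate these, and whether it penalises either depends on a definition that the reader does not have. On each of the two readings that come most naturally, one kind of poor detector can reach 90%, so a report that the goal was met could support an unsound conclusion about the feedback. If the definition is settled only after the data are seen, the choice of definition can also decide the result. Separately, without an interval an observed 90% looks the same whether it rests on 20 errors or 200.

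**Working it through.** The 90% is a target with no derivation and no event count, so there is no plan figure to reproduce. The 36 and 35 subjects in the SAP's power section concern head range of motion and head velocity, not this objective.

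**Inputs from the documents:** threshold 90% per error type; clinician as reference; app errors time-stamped; the clinician records errors, with no mention of error-free repetitions.

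**Assumed, because the documents give none:** share p of scored units that contain the error (5%, 10%, 20%); detector sensitivity and specificity; 20 to 200 errors per type; for clustering, 5 errors per affected participant and an intraclass correlation (ICC) of 0.2.

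**Notation:** TP = marked and flagged; FN = marked, not flagged; FP = flagged, not marked; TN = neither.

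**1. Share of clinician-marked errors found, TP/(TP+FN).** This is closest to the SAP's wording. FP does not appear, so always flagging scores 100%. What it hides is PPV = sens·p / [sens·p + (1−spec)(1−p)].

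| Detector | Score | PPV at p = 5% | 10% | 20% |
|---|---|---|---|---|
| Always flags | 100% | 5% | 10% | 20% |
| Sens 92%, spec 70% | 92% | 0.046/0.331 = 14% | 0.092/0.362 = 25% | 0.184/0.424 = 43% |

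**2. Share of all units correct, sens·p + spec·(1−p).**

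| Detector | p = 5% | 10% | 20% |
|---|---|---|---|
| Never flags (score 1−p) | 95% | 90% | 80% |
| Sens 40%, spec 97% | 94.15% | 91.3% | 85.6% |

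Never flagging meets the goal when p is at most 10%. The second detector meets it up to p = 0.07/0.57 = 12.3%. Both fail at 20%. This reading also needs a count of error-free units, which the Protocol does not ask the clinician to record.

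**3. A reading that penalises both faults, TP/(TP+FP+FN).** Never flagging scores 0. Always flagging scores p, that is 5% to 20%. Neither reaches 90%.

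**4. The same data under each definition.** Take 1000 units, 100 with the error, 90 hits, 10 misses and 90 false alerts, so TN = 810.
- Share of marked errors found: 90/100 = 90%.
- Share of all units correct: (90 + 810)/1000 = 90%.
- PPV: 90/180 = 50%.
- TP/(TP+FP+FN): 90/190 = 47.4%.

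The goal is met on two definitions and clearly missed on the third.

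**5. Precision.** The Wilson 95% limits are [p̂ + z²/2n ± z√(p̂(1−p̂)/n + z²/4n²)] / (1 + z²/n), with z = 1.96.
- 18/20: 70% to 97%.
- 45/50: (0.9384 ± 1.96 × √(0.0018 + 0.000384)) / 1.0768, that is 79% to 96%.
- 180/200: 85% to 93%.
- 45/50 with clustering: design effect 1 + (5−1) × 0.2 = 1.8, effective n = 50/1.8 = 27.8, giving 74% to 97%.

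If the true proportion is 85%, the chance of observing at least 90% is as follows (binomial if independent; beta-binomial with the clustering assumed above).

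| Errors | 20 | 50 | 100 | 200 |
|---|---|---|---|---|
| Independent | 40% | 22% | 10% | 2.5% |
| Clustered | 46% | 30% | 18% | 7% |

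**The case against.** **Hypothesis 1 may supply the definition.** This stands. The SAP refers to it, and the power section draws on Phase I data, so the text may sit in an earlier plan (an inference). A reader might infer that the metric was never defined. The documents support only that it is not reproduced here. Even if it is defined elsewhere, no interval is planned for Hypothesis 5.

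**Other ordinary readings do not fail.** This also stands. TP/(TP+FP+FN) stops both extreme detectors, but neither document states it. A reader might also infer that one definition lets through both kinds of poor detector. It does not: the first reading admits over-flagging only, and the second admits under-flagging only, and then only for infrequent errors.

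**It is a proof of concept.** The Protocol says so: "This experiment will test the app for proof of concept on older subjects with dizziness". Its stated aims are similar performance with and without the app, and usability and enjoyment. A descriptive goal is reasonable in that setting, and the absence of a hypothesis test is not a fault. A descriptive proportion still needs a numerator, a denominator and some indication of precision.

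**The illustrations are assumed.** They are. Frequencies, counts, clustering and detector properties are not in the documents, and the always-flag and never-flag detectors are limiting cases. They show what the criterion would allow. They are not evidence that this app performs poorly.

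**Conclusion.** The point holds in a limited form. As written in these documents, the Hypothesis 5 criterion does not fix what is measured. On the reading closest to the wording, a detector with many false alerts meets 90%. On the all-units reading, a detector that never flags meets it when the error occurs in at most 10% of units. The gap in definition does not depend on the assumed numbers; its practical size does. The missing interval matters most for infrequent error types: an observed 90% is compatible with roughly 70% to 97% at 20 independent errors and 79% to 96% at 50, and the range is wider if errors cluster within participants.

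This affects how one descriptive objective is read, not the validity of the study. It is a cheap improvement that should be made, at the lower end of that grade.

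**What to change.** For each error type, replace the single accuracy figure with two proportions that need no error-free units:

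- **Sensitivity:** the share of clinician-marked errors that have a matching app alert.
- **PPV:** the share of app alerts that match a clinician-marked error.

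Specify the matching before the data are examined: a fixed time window; a continuing error counts as one error; repeated alerts within that same error count as one matched alert; other unmatched alerts are false alarms. The rule on repeats is needed because two alerts on one continuing error, with only the first matched, would give a PPV of 1/2 with no false detection.

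Keep 90% as a descriptive goal, with no test and no pass rule on a lower limit. Do not describe it as met on sensitivity alone without PPV beside it. This makes false alarms visible; it does not set a limit on them.

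Give each proportion a 95% interval that allows for several events per participant. A participant-level bootstrap would do. Where the observed value is at or near 100%, a Wilson interval on an effective sample size, n/[1+(m−1)·ICC] with m events per participant, is more usable. Any ICC would be an assumption to declare in advance; a fixed 0.2 is optional.

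If the Hypothesis 1 method already defines the metric, reproduce it in the SAP and still add PPV and the interval.

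**Cost.** No new data collection is needed. The Protocol mentions time stamps only for the app's errors, so clinician error times must be taken from the video and aligned with the app clock. Intervals will be wide for rare errors. PPV depends on how often errors occur in this sample, and an error that the clinician overlooks counts as a false alarm.
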